A. Will adults be enrolled ?

Yes

1. What is the age range of the adult subjects?

Young adults aged 19-29

2. What is the rationale for selecting this age range?

As vaping is prevalent in youth and young adult population, the objective of this study is to test the application of financial and social support to improve the reach, engagement and retention of the vaping cessation program consisting of education lessons and text-messaging support program, which are developed and tested specially among youth and young adult populations.

In general, young adults are referred to adults aged between 18-20 years-old. In Nebraska, an individual is considered an adult when he/she reaches the age of 19.

B. Will children (18 years of age or younger) be included in this research?

No

1. What is the justification for excluding children from participating in this research?

Research is irrelevant to children (e.g. disease or condition rarely encountered in children). Knowledge being sought in the research is already available for children or will be obtained from another ongoing study.

♦ A separate study in children is warranted and preferable.

Insufficient data are available in adults to judge the potential risk in children.

Other. Explain.

7. Race and Ethnicity

Are there any subject enrollment restrictions based upon race or ethnic origin?

No

8. Vulnerable Subjects

A. Will prisoners be included in the research?

No

B. Select from the list all of the vulnerable populations that will specifically be recruited to participate in this research.

Decisionally-impaired persons

Critically ill patients

Students of the investigator

Employees of the investigator

Educationally disadvantaged individuals

Socially or economically disadvantaged individuals

Individuals with a stigmatizing illness or condition

Individuals from a marginalized social or ethnic group

Other.

♦ No vulnerable subjects will be specifically recruited

9. Inclusion Criteria

What are the specific inclusion criteria?

- Aged 19-29
- Self-report current e-cigarette users (in the past 30 days)
- Have access to internet/video chat/SMS text message
- Are interested in quitting vaping in the next 30 days

10. Exclusion Criteria

What are the specific exclusion criteria?

- Must meet all the inclusion criteria
- Self-report as currently pregnant or planning to become pregnant in the next 3 months
- Already involved in vaping cessation programs (either behavioral or medical intervention)

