As this is a incentive-based (financial and social) enhanced vaping cessation study, there will not be therapeutic interventions or treatments other than educational lessons and support programs. Breastfeeding should not be impacted.

METHODS AND PROCEDURES

12. Methods and Procedures Applied to Human Subjects

A. Are there any evaluations or tests that will be performed for the purpose of determining subject eligibility which would not be routinely conducted as part of standard clinical care of the prospective subject?

Yes

1. Describe the evaluations or tests to determine subject eligibility

Interested potential participants will complete an online screen survey (RedCap link embedded in the recruitment email), to determine their eligibility based on the inclusion and exclusion criteria.

2. Are any of these evaluations or tests performed prior to obtaining informed consent?

Yes

B. Describe the research plan, including all procedures, interventions, evaluations and tests.

Study design

This study employs a pilot, 4-arm randomized clinical trial (RCT) design. Individuals who meet the eligibility criteria will be randomized (1:1:1:1) to receive one of the following interventions with a 1-month quitting preparation phase and a 2-month abstinence phase:

1) Active control-

Participants in this arm will receive an evidence-based text-messaging support

2) Media literacy-

Participants will receive media literacy e-learning lessons and an evidence-based text-messaging support

3) Financial incentive-

Participants will receive financial incentive intervention and an evidence-based text-messaging support

4) Combined-

Participants will receive media literacy e-learning lessons, financial incentive, and an evidence-based text-messaging support program

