For quality improvement and future modification and adoption of the multi-component vaping cessation program, we will conduct an exit interview (n=8-12; n=2-3 from each arm based on first available participants) via a video call, with participants to identify the feasibility, facilitators, and barriers of implementing the proposed interventions. Participant who have completed the end-of-study assessment will be contacted by research staff for their willingness to participate in the exit interview. The interview will take place after the Week 12 visit based on participant's availability via a zoom meeting. Therefore, the total participating time in the study is roughly 14-16 weeks. The interview will be audio-recorded and transcribed in order to produce an accurate transcript of the discussion. Each participant in the exit interview will receive a \$25.00 giftcard. The interview will last less than 30 minutes.

Participant enrollment process

Interested potential participants will complete an online screen survey (RedCap link embedded in the recruitment email; and less than 5 minutes to complete), to determine their eligibility based on the inclusion and exclusion criteria. Once potential participants have been deemed as eligible through screening questions, participants will be asked if they would like to participate. If they agree, they will be asked to indicated the times and days that participants would be available to attend the in-person session to complete the informed consent, intake process, including providing saliva sample, urine sample (only for 20 participants who volunteer to be in the biomarker measurement group), and completing the baseline survey (less than 20 minutes to complete), consisting of demographic information, vaping history, vaping experience/behavior, exposure to Tobacco Marketing and Marketing Influences, social efficacy, UPPS impulsive behavior scale, money choice question, and nicotine dependence index (Penn State Cigarette Dependence Index). After completing all the tasks at the baseline session, a randomization algorithm will be utilized to decide which interventions (*Active control, Media literacy, financial incentive, and Combined*) that a participant will be assigned to.

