2. Baseline and end-of-study survey, including demographic, vaping history, vaping experience/behavior, attempt to quit, Penn State Nicotine Dependence Index, exposure to Tobacco Marketing and Marketing Influences, UPPS impulsive behavior scale, money choice question, and self-efficacy about not to vape, and wheezing and related respiratory symptoms

Primary outcome

- **biochemically verified vaping abstinence** (negative results- will be cut-off < 30 ng/mL⁷¹), measured by saliva cotinine samples at the Week 12 visit.

Secondary outcome

1. Nicotine abstinence: bi-weekly/monthly saliva nicotine abstinence results (positive vs. negative) will be obtained using the iScreen test kit ([https://stat-technologies.com/product/alere-iscreen-for-cotinine/#:~:text=The%20Alere%20iScreen%C2%AE%20OFD,nicotine\)%20in%20human%20oral%20fluid.](https://stat-technologies.com/product/alere-iscreen-for-cotinine/#:~:text=The%20Alere%20iScreen%C2%AE%20OFD,nicotine)%20in%20human%20oral%20fluid.)) after the target quit date for 2 month in addition to baseline and Week 12 saliva cotinine samples. Saliva sample/results will be collect in person at baseline and Week 12 visits and remotely via live video calls during the abstinence phase. The remote saliva sample collection will follow the instruction below:

- Participants will open the new, labeled packaging for each testing kit while on the video call to ensure they are using a new test each time
- Participants will be asked to write down the participants id, test number, date, and time on the test kit
- Participants will take a picture, including participant id, test number, date, and time for verifying the final results and provide the final results and picture to the research

staff before ending the call (approximately 10-minute processing time) All participant will need to provide a saliva sample at the in-person baseline and the Week 12 visits and at remote video calls (Week 6, Week 8, and Week 10).

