2. Biomarkers of toxic exposures: Twenty participants who are assigned the biomarker measurement group will need to provide the urine sample at the in-person baseline (Week 0) and Week 12) visits at the UNMC clinical research center (CRC). The nurse research coordinator at CRC would assist with the urine sample collection. The biomarker classes may include: 1) cotinine and hydroxycotinine, and 2) creatinine. The biomarker testing of toxic exposure is solely for research purpose and thus the results will not be share with the participants.

3. Engagement, assessed by: a) proportions of media literacy e-learning lessons completed at the end of the quitting preparation phase (Week 4), and b) proportions of participants who submitted the remote saliva cotinine sample at each scheduled time-point at Week 12;

4. Nicotine dependence index, measured by the Penn State E-cigarette Dependence (PSECD) index at baseline and Week 12;

5. Media literacy, measured by the vaping media literary scale at baseline and Week 12.

4) Self-reported vaping abstinence, assessed by the question In the past 30 days, did you vape at all, even a puff of someone else? at Week 12.

Exploratory outcomes

We will collect intervention cost data using all program invoices related to program implementation and survey questionnaire to estimate the cost-effectiveness of the program. For example, we will calculate the incremental cost per additional completing the vaping cessation program, the incremental cost per additional abstinence case across study arms.

C. Select any of the following that apply to the research:

Phase I study

♦ Randomization

Placebo (or non-treatment arm)

Washout

Sensitive surveys or questionnaires

None of the above

Option chosen: Randomization

Describe randomization process and schedule

Participants will be assigned following a randomization table created by the study statistician after completing the consent process and baseline survey on the REDCap platform. To

ensure an even distribution of participants between the four intervention groups, eligible subjects will be randomly assigned to one of four intervention groups using a computer generated randomization table created by the study statistician. We will recruit 5 participants from each intervention group (until fulfilled) for the biomarker measurement group.

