UNMC offers a nicotine dependence clinic (cigarettes, dip, other forms of nicotine products) that has dependence counseling services with a qualified professional. Clinicians at this clinic offer counseling, pharmacotherapy (nicotine replacement therapy), and lung screening for high-risk patients. Services are offered at a cost.

2. Is the potential benefit of the research at least as good as the potential benefits of the alternatives described above?

Yes

3. Are there any reasonably available alternatives outside this institution which would have the potential for providing benefit to the subjects outside the research context?

Yes

a. What are the reasonably available alternatives?

Other institutions have similar nicotine dependence clinics similar to the clinic described above.

4. Would any of the study procedures or courses of treatment in the protocol be available to the subject if they elected not to participate?

Yes

a. Explain.

Participants who choose not to participate or withdraw from the study, will still have access to the SMS text-based quitting support program (This is Quitting), and cotinine testing (saliva samples).

5. Would the research intervention be available outside the context of research?

Yes

6. Are there any treatments that the subject would be denied as a consequence of participating in research that he/she would have received had he/she not participated?

No

7. How do the risks of the research compare with the risks of alternative procedures or courses of treatment described above?

There are some risks associated with pharmacotherapy (nicotine replacement) treatment that may be applicable to the treatment options mentioned above. Given that this study simply includes ono-invasive interventions- media literacy e-learning lessons, text-messaging support programs, and financial incentives, the risk of research is minimal or

comparable to the risk of alternate procedures.

FINANCIAL OBLIGATIONS AND COMPENSATION

22. Financial Obligations of the Subject

A. Who will pay for research procedures, interventions, evaluations and tests? Check all that apply.

Sponsor

◆ Grant

CRC, CCTR

Costs or fees waived by Nebraska Medicine, UNMC- P, CHMC or CSP

Department/Section funds

◆ Other. Explain faculty fund

B. Will any of the research procedures, interventions, evaluations and tests described above be charged to the Subject, the Subject's health insurance, or Medicare/Medicaid?

No

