Interested individuals will complete an online screening through RedCap to determine their eligibility prior to informed consent. Screening questions includes current age, frequency of vaping, access to internet/video chat/SMS text message or not, and intention/desire to quit.

B. Will the investigator make the initial contact with the potential subject to tell him/her about the research (for example, by contacting existing or past previous patients or research participants; or by contacting prospective subjects thru school records, or thru support groups or other Interest Groups; or thru use of the Hospital Opt-In Database)?

Yes

1. How will prospective subjects be identified?

We will work with UNMC EHR data access core to identify a potential participant pool. A recruitment/screening email will be sent to patients aged 19-29 with an opt-in for research indication through the Epic patient portal.

2. Will potential subjects be screened for eligibility prior to informed consent?

Yes

a. What information will be collected prior to informed consent?

Interested individuals will complete an online screening through RedCap to determine their eligibility prior to informed consent. Screening questions includes current age, frequency of vaping, access to internet/video chat/SMS text message or not, and intention/desire to quit.

b. By whom?

Interested individuals will complete an online screening through RedCap by themselves to determine their eligibility prior to informed consent. If an interested individuals contacts the research team because of the recruitment flyer or other mode (e.g., social media) outside of the recruitment email (e.g., see the flyer in the community), the research staff, listed on the IRB protocol will conduct the phone screening using the RedCap to determine his/her eligibility. If the individual is eligible, the research staff will obtain a verbal consent from the individual and enroll him/she in the study and email him/her a copy of informed consent.

c. Does that person have ethical access to information about potential subjects?

Yes

i. Describe

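### The primary outcome calls a nicotine test vaping abstinence, and no item on other nicotine use is specified, so some people who stop vaping are scored as failures, possibly unequally by arm

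*Combined protocol and SAP*

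**What the plan says.** **Outcome.** Section 12.B (Primary outcome) defines biochemically verified vaping abstinence by saliva cotinine below 30 ng/mL at Week 12. Under Secondary outcome, item 1 is headed nicotine abstinence and states that "saliva nicotine abstinence results (positive vs. negative) will be obtained using the iScreen test kit"; that item includes the Week 12 sample. Self-reported vaping over the past 30 days at Week 12 is a separate secondary outcome and is not combined with cotinine.

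**Entry.** Section 9 requires "Self-report current e-cigarette users (in the past 30 days" and sets no condition on cigarettes or other nicotine products. The only exclusion in section 10 that bears on nicotine replacement is "Already involved in vaping cessation programs (either behavioral or medical intervention".

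**Nicotine replacement after entry.** Section 21 describes it as available locally. To the form question "Are there any treatments that the subject would be denied as a consequence of participating in research" the protocol answers No.

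**What is asked.** Section 25 summarises screening: "Screening questions includes current age, frequency of vaping, access to internet/video chat/SMS text message or not, and intention/desire to quit". Section 12.B lists the baseline and end-of-study survey contents and describes the video calls. None of these names an item on other nicotine products or nicotine replacement. The enrollment text lists a "nicotine dependence index (Penn State Cigarette Dependence Index". The survey list calls the instrument a Nicotine Dependence Index, and secondary outcome 4 has dependence "measured by the Penn State E-cigarette Dependence (PSECD) index at baseline and Week 12".

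**Incentive.** In the Financial incentive and Combined arms only, each sample earns $3. A negative sample earns a further $7, $12, $17 or $22, reset to $7 after a missing or positive sample.

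**Analysis.** Section 12.E adjusts for age, gender and race/ethnicity.

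**The concern.** Cotinine reflects nicotine intake from any source. A dual user who gives up e-cigarettes but goes on smoking, or a participant who stops vaping with the help of nicotine replacement, can test positive and be scored as not abstinent from vaping. That lowers the observed abstinence rate and shrinks any real difference between arms.

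The error need not be the same in every arm. The bonus is paid for a negative cotinine result, so it rewards giving up all nicotine, and only two arms receive it. Hypothesis 1 in section 2 compares Combined with Media literacy as well as with Financial incentive. The first of these is an incentive versus no-incentive contrast. Part of a difference there could reflect less smoking or less nicotine replacement rather than less vaping. The cost per additional abstinence case under Exploratory outcomes would inherit the same ambiguity if it uses this endpoint.

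**Working it through.** **The plan's own figures.** The sample size rests on a rule of thumb, with no abstinence rates, effect size or power to reproduce. Its arithmetic is consistent: 4 × 20 = 80, above 4 × 12 = 48 and above 70. The maximum incentive also reproduces: 4 × $3 + $7 + $12 + $17 + $22 = $70.

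**Inputs.** From the documents: 20 per arm, two incentive and two non-incentive arms, significance level 0.05 (taken as two-sided). Assumed, because the documents give nothing: the true vaping-quit rate t (20% to 40%), and the share m of vaping quitters who are cotinine-positive from another source (10% to 40%). Continuing vapers are assumed to test positive.

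**Formula.** Observed cotinine-negative rate = t × (1 − m). With the same t in both groups, the spurious difference = t × (m without incentive − m with incentive).

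**No true difference in vaping.** Rejection rates come from exact enumeration of the uncorrected chi-square test. The 40 versus 40 column pools the two incentive and the two non-incentive arms, as an illustration.

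| t | m without / with incentive | Observed rates | Spurious difference | Rejection, 20 per arm | Rejection, 40 vs 40 |
|---|---|---|---|---|---|
| 30% | 20% / 20% | 24% vs 24% | 0 points | 5.1% | 5.0% |
| 20% | 20% / 10% | 16% vs 18% | 2 points | 5.3% | 5.9% |
| 30% | 30% / 10% | 21% vs 27% | 6 points | 7.3% | 9.6% |
| 40% | 30% / 10% | 28% vs 36% | 8 points | 8.8% | 11.6% |
| 40% | 40% / 10% | 24% vs 36% | 12 points | 13.6% | 21.1% |

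In the 30% row with shares 30% / 10%, the quitters counted as failures number 40 × 0.30 × 0.30 = 3.6 without the incentive and 40 × 0.30 × 0.10 = 1.2 with it, per 40 participants.

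**Equal shares in both groups.** There is no spurious difference, only dilution. A true 20% versus 40% gives (0.40 − 0.20) × (1 − m) = 18, 16 or 14 points for m = 10%, 20% or 30%. For a true 20% versus 50%, power by normal approximation is:

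| m | Observed rates | Power, 20 per arm | Power, 40 vs 40 |
|---|---|---|---|
| 0% | 20% vs 50% | 51% | 82% |
| 20% | 16% vs 40% | 39% | 67% |
| 40% | 12% vs 30% | 28% | 51% |

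Exact enumeration agrees with these to within 2 percentage points.

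**What the planned data can separate.** Crossing Week 12 cotinine with the self-reported vaping question isolates participants who deny vaping but test positive. It cannot show whether they used another product or reported inaccurately. The urine panel covers only 20 participants and lists cotinine, hydroxycotinine and creatinine, none of which is described as identifying the source of nicotine.

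**The case against.** Three stronger readings are tempting, and the documents do not support them.

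- *The trial never asks about other nicotine.* This cannot be shown. The questionnaires are not in the documents, and the lists are open-ended. The screening list is visibly incomplete: section 12.A says that screening serves "to determine their eligibility based on the inclusion and exclusion criteria", yet pregnancy and cessation-program involvement are not on it. A cigarette dependence index is named once at baseline. The texting program asks about product usage, though this is not listed as trial data. What can be said is that no such item is specified, in particular none at Week 12.
- *Quitters who use other nicotine cannot be told apart from continuing vapers.* The Week 12 self-report does reveal the discordant group. What it leaves open is the cause.
- *Entry admits nicotine replacement users generally.* Use within a cessation program at entry is excluded. Use outside a program, or begun later, is not addressed.

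It is also fair to say that no document shows a difference by arm. The incentive totals at most $70, and the 8-point case needs a threefold gap in other nicotine use (30% versus 10%), which is an assumption. In an arm of 20, 8 points is 1.6 participants. The error can also run the other way: entry does not require nicotine-containing liquid, and someone vaping without nicotine could test negative. Finally, this is a feasibility pilot with no power claim, and cotinine is a defensible endpoint for abstinence from nicotine.

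These points limit the size and certainty of the concern but do not remove it. Aim 2 seeks a preliminary effect on vaping abstinence, and the endpoint as labelled does not measure that. If abstinence from all nicotine is what is meant, the label should say so.

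**Conclusion.** The point holds in a limited form. Following the plan as written, a participant who stops vaping but is cotinine-positive from another source is scored as a vaping failure, and no specified item would explain the result. Because only two arms are paid for negative cotinine, the error may be unequal, including in Combined versus Media literacy. Combined versus Financial incentive is less exposed, since both arms carry the same payment.

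The size rests wholly on assumed rates: about 2 to 12 points of spurious difference for quit rates of 20% to 40% and shares from 20% versus 10% up to 40% versus 10%. The corresponding false-positive rates are about 5% to 14% at 20 per arm and 6% to 21% at 40 versus 40. With equal shares there is dilution and lost power only. The difference is spurious only as a statement about vaping; as a statement about nicotine it would be real, which is why the label matters. In a pilot of this size the harm is mainly to interpretation. The change is worth making but is not a bar to running the trial.

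**What to change.** 1. Add one item on cigarettes, other nicotine products and nicotine replacement, with a stated recall period (for example, past 30 days at baseline and past 7 days afterwards), at baseline and at each cotinine test (Weeks 6, 8, 10 and 12).
2. Keep the Week 12 cotinine result as the primary outcome, but describe it as nicotine abstinence in the outcome definition and in the conclusions.
3. Pre-specify one sensitivity table by arm that crosses Week 12 cotinine with self-reported vaping and other nicotine use. Show the arm comparison as observed and again with participants who report no vaping, report other nicotine use and test positive reclassified as not vaping. With 20 per arm, present counts rather than rely on tests.
4. Name the dependence instrument consistently throughout section 12.B.

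**Cost.** One question at five contacts that already exist, one table and wording edits. Recruitment, the cotinine test, the incentive schedule and participants' care are unchanged. The main drawback is that reclassification relies on self-report in an unmasked trial, so it should remain a sensitivity analysis and not replace the biochemical result. The item has to be asked at the time, because other nicotine use would be hard to reconstruct afterwards.
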